5.1.3 Subject Exclusion Criteria

The subject must be excluded from participating in the trial if the subject:

1. Is **currently participating** and receiving study therapy, or has participated in a study of an investigational agent and received study therapy **or used** an investigational device **within 4 weeks** of the first dose of treatment.

Note: Subjects who have entered the follow-up phase of an investigational study may participate as long as it has been 4 weeks since the last dose of the previous investigational agent or device.

2. Has an active autoimmune disease that has required systemic treatment in past 2 years (i.e. with use of disease modifying agents, corticosteroids or immunosuppressive drugs). Replacement therapy (eg., thyroxine, insulin, or physiologic corticosteroid

replacement therapy for adrenal or pituitary insufficiency, etc.) is not considered a form of systemic treatment.

3. Has a diagnosis of immunodeficiency or is receiving systemic steroid therapy or any other form of immunosuppressive therapy within 7 days prior to the first dose of trial treatment.
4. Has had a prior anti-cancer monoclonal antibody (mAb) for direct anti-neoplastic treatment within 4 weeks prior to study Day 1 or who has not recovered (i.e., \leq Grade 1 or at baseline) from adverse events due to agents administered more than 4 weeks earlier.
5. Has had prior chemotherapy, targeted small molecule therapy, or radiation therapy within at least 2 weeks prior to study Day 1 or who has not recovered (i.e., \leq Grade 1 or at baseline) from adverse events due to a previously administered agent.

Note: Subjects with \leq Grade 2 neuropathy or alopecia of any grade are an exception to this criterion and may qualify for the study.

Note: If subject received major surgery, they must have recovered adequately from the toxicity and/or complications from the intervention prior to starting therapy.

6. Has a known additional malignancy that progressed or required active treatment within the last 5 years. Exceptions include basal cell carcinoma of the skin, squamous cell carcinoma of the skin that has undergone potentially curative therapy, or in situ cervical cancer.
7. Has radiographically detectable (even if asymptomatic and/or previously treated) central nervous system (CNS) metastases and/or carcinomatous meningitis. Brain imaging at screening is required.
8. Has a history of (non-infectious) pneumonitis that required steroids or current pneumonitis or a history of interstitial lung disease..
9. Has an active infection requiring systemic therapy.
10. Has a history or current evidence of any condition, therapy, or laboratory abnormality that might confound the results of the trial, interfere with the subject's participation for the full duration of the trial, or is not in the best interest of the subject to participate, in the opinion of the treating investigator.
11. Has known psychiatric or substance abuse disorders that would interfere with cooperation with the requirements of the trial.
12. Is pregnant or breastfeeding, or expecting to conceive or father children within the projected duration of the trial, starting with the screening visit through 120 days after the last dose of trial treatment.
13. Has received prior therapy with an anti-PD-1, anti-PD-L1, anti-PD-L2 agent or with an agent directed to another co-inhibitory T-cell receptor (e.g. CTLA-4, OX-40, CD137) or has participated in Merck MK-3475 trials.
14. Has a known history of Human Immunodeficiency Virus (HIV) (HIV 1/2 antibodies).

15. Has known active Hepatitis B (e.g., HBsAg reactive) or Hepatitis C (e.g., HCV RNA [qualitative] is detected).

16. Has received a live vaccine within 30 days of planned start of study therapy.

Note: Seasonal influenza vaccines for injection are generally inactivated flu vaccines and are allowed; however intranasal influenza vaccines (e.g., Flu-Mist®) are live attenuated vaccines, and are not allowed.

17. Is or has an immediate family member (e.g., spouse, parent/legal guardian, sibling or child) who is investigational site or sponsor staff directly involved with this trial, unless prospective IRB approval (by chair or designee) is given allowing exception to this criterion for a specific subject.

5.2 Trial Treatment(s)

The treatment to be used in this trial is outlined below in [Table 3](#).

Table 3 Trial Treatment

Drug	Dose	Dose Frequency	Route of Administration	Regimen/Treatment Period	Use
Pembrolizumab	200 mg	Q3W	IV infusion	Day 1 of each 3 week cycle	Experimental

Trial treatment should begin on the day of randomization or as close as possible to the date on which the subject is allocated/assigned.

Study drug should be administered on Day 1 of each 3 week cycle after all procedures/assessments have been completed as detailed on the Trial Flow Chart (Section 6.0).

Pembrolizumab will be administered as a 30 minute IV infusion every 3 weeks. Sites should make every effort to target infusion timing to be as close to 30 minutes as possible.

The investigator shall take responsibility for and shall take all steps to maintain appropriate records and ensure appropriate supply, storage, handling, distribution and usage of trial treatments in accordance with the protocol and any applicable laws and regulations.

5.2.1 Dose Selection/Modification

5.2.1.1 Dose Selection (Preparation)

The rationale for selection of doses to be used in this trial is provided in Section 4.0 – Background & Rationale. Details on preparation and administration of pembrolizumab are provided in the Pharmacy Manual.

5.2.1.2 Dose Modification (Escalation/Titration/Other)

Pembrolizumab dose reductions are not applicable to this study. However, pembrolizumab must be withheld for drug-related toxicities and severe or life-threatening AEs as described in [Table 4](#) below. If a dose must be held/delayed do not complete a cycle visit until the subject is dosed again. When pembrolizumab is restarted, this dose would be considered Day 1 of the missed cycle.

Adverse events (both non-serious and serious) associated with pembrolizumab exposure may represent an immunologic etiology. These immune-related adverse events (irAEs) may occur shortly after the first dose or several months after the last dose of treatment and may affect more than one body system simultaneously. Therefore, early recognition and initiation of treatment is critical to reduce complications. Based on existing clinical trial data, most irAEs were reversible and could be managed with interruptions of pembrolizumab, administration of corticosteroids and/or other supportive care. For suspected irAEs, ensure adequate evaluation to confirm etiology or exclude other causes. Additional procedures or tests such as bronchoscopy, endoscopy, skin biopsy may be included as part of the evaluation. Based on the severity of irAEs, withhold or permanently discontinue pembrolizumab and administer corticosteroids. Dose modification and toxicity management guidelines for irAEs associated with pembrolizumab are provided in [Table 4](#). See Section 5.6 for supportive care guidelines, including use of corticosteroids.

Table 4 Dose Modification and Toxicity Management Guidelines for Immune-related AEs Associated with Pembrolizumab

General instructions:				

 1. Corticosteroid taper should be initiated upon AE improving to Grade 1 or less and continue to taper over at least 4 weeks. 2. For situations where pembrolizumab has been withheld, pembrolizumab can be resumed after AE has been reduced to Grade 1 or 0 and corticosteroid has been tapered. Pembrolizumab should be permanently discontinued if AE does not resolve within 12 weeks of last dose or corticosteroids cannot be reduced to ≤ 10 mg prednisone or equivalent per day within 12 weeks. 3. For severe and life-threatening irAEs, IV corticosteroid should be initiated first followed by oral steroid. Other immunosuppressive treatment should be initiated if irAEs cannot be controlled by corticosteroids. 				
Immune-related AEs	Toxicity grade or conditions (CTCAEv4.0)	Action taken to pembrolizumab	irAE management with corticosteroid and/or other therapies	Monitor and follow-up
Pneumonitis	Grade 2	Withhold	
 • Administer corticosteroids (initial dose of 1-2 mg/kg prednisone or equivalent) followed by taper 	
 • Monitor subjects for signs and symptoms of pneumonitis • Evaluate subjects with suspected pneumonitis with radiographic imaging and initiate corticosteroid treatment • Add prophylactic antibiotics for opportunistic infections
	Grade 3 or 4, or recurrent Grade 2	Permanently discontinue		
Diarrhea / Colitis	Grade 2 or 3	Withhold	
 • Administer corticosteroids (initial dose of 1-2 mg/kg prednisone or equivalent) followed by taper 	
 • Monitor subjects for signs and symptoms of enterocolitis (ie, diarrhea, abdominal pain, blood or mucus in stool with or without fever) and of bowel perforation (ie, peritoneal signs and ileus). • Subjects with \geq Grade 2 diarrhea suspecting colitis should consider GI consultation and performing endoscopy to rule out colitis. • Subjects with diarrhea/colitis should be advised to drink liberal quantities of clear fluids. If sufficient oral fluid intake is not feasible, fluid and electrolytes should be substituted via IV infusion.
	Grade 4	Permanently discontinue		

Immune-related AEs	Toxicity grade or conditions (CTCAEv4.0)	Action taken to pembrolizumab	irAE management with corticosteroid and/or other therapies	Monitor and follow-up
AST / ALT elevation or Increased bilirubin	Grade 2	Withhold	
 Administer corticosteroids (initial dose of 0.5- 1 mg/kg prednisone or equivalent) followed by taper 	
 Monitor with liver function tests (consider weekly or more frequently until liver enzyme value returned to baseline or is stable)
	Grade 3 or 4	Permanently discontinue	
 Administer corticosteroids (initial dose of 1-2 mg/kg prednisone or equivalent) followed by taper 	
Type 1 diabetes mellitus (T1DM) or Hyperglycemia	Newly onset T1DM or Grade 3 or 4 hyperglycemia associated with evidence of β -cell failure	Withhold	
 Initiate insulin replacement therapy for subjects with T1DM Administer anti-hyperglycemic in subjects with hyperglycemia 	
 Monitor subjects for hyperglycemia or other signs and symptoms of diabetes.
Hypophysitis	Grade 2	Withhold	
 Administer corticosteroids and initiate hormonal replacements as clinically indicated. 	
 Monitor for signs and symptoms of hypophysitis (including hypopituitarism and adrenal insufficiency)
	Grade 3 or 4	Withhold or permanently discontinue ¹		
Hyperthyroidism	Grade 2	Continue	
 Treat with non-selective beta-blockers (eg, propranolol) or thionamides as appropriate 	
 Monitor for signs and symptoms of thyroid disorders.
	Grade 3 or 4	Withhold or permanently discontinue ¹		
Hypothyroidism	Grade 2-4	Continue	
 Initiate thyroid replacement hormones (eg, levothyroxine or liothyronine) per standard of care 	
 Monitor for signs and symptoms of thyroid disorders.
Nephritis and Renal dysfunction	Grade 2	Withhold	
 Administer corticosteroids (prednisone 1-2 mg/kg or equivalent) followed by taper. 	
 Monitor changes of renal function
	Grade 3 or 4	Permanently discontinue		

Immune-related AEs	Toxicity grade or conditions (CTCAEv4.0)	Action taken to pembrolizumab	irAE management with corticosteroid and/or other therapies	Monitor and follow-up
Myocarditis	Grade 1 or 2	Withhold	
 Based on severity of AE administer corticosteroids 	
 Ensure adequate evaluation to confirm etiology and/or exclude other causes
	Grade 3 or 4	Permanently discontinue		
All other immune-related AEs	Intolerable/persistent Grade 2	Withhold	
 Based on type and severity of AE administer corticosteroids 	
 Ensure adequate evaluation to confirm etiology and/or exclude other causes
	Grade 3	Withhold or discontinue based on the type of event. Events that require discontinuation include and not limited to: Guillain-Barre Syndrome, encephalitis		
	Grade 4 or recurrent Grade 3	Permanently discontinue		

AE=adverse event; ALT=alanine aminotransferase; AST= aspartate aminotransferase; CTCAE= Common Toxicity Criteria for Adverse Events; GI=gastrointestinal; irAE=immune related adverse event; IV=intravenous; T1DM=Type 1 diabetes mellitus.

1. Withhold or permanently discontinue pembrolizumab is at the discretion of the investigator or treating physician.

NOTE:
For subjects with Grade 3 or 4 immune-related endocrinopathy where withhold of pembrolizumab is required, pembrolizumab may be resumed when AE resolves to \leq Grade 2 and is controlled with hormonal replacement therapy or achieved metabolic control (in case of T1DM).

Dosing interruptions are permitted in the case of medical / surgical events or logistical reasons not related to study therapy (e.g., elective surgery, unrelated medical events, patient vacation, and/or holidays). Subjects should be placed back on study therapy within 3 weeks of the scheduled interruption, unless otherwise discussed with the Sponsor. The reason for interruption should be documented in the patient's study record as well as in the Sponsor data collector.

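### Table 4 gives two answers for Grade 1 myocarditis, and it lets controlled Grade 2 hypophysitis resume only if the event began at Grade 3 or 4

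*Combined protocol and SAP*

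**What the plan says.** Section 5.2.1.2 rules out dose reduction and requires withholding as set out in Table 4. The relevant parts of the table are these.

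- **General instruction 1:** "Corticosteroid taper should be initiated upon AE improving to Grade 1 or less and continue to taper over at least 4 weeks".
- **General instruction 2:** once a dose has been withheld, "pembrolizumab can be resumed after AE has been reduced to Grade 1 or 0 and corticosteroid has been tapered". It adds that "Pembrolizumab should be permanently discontinued if AE does not resolve within 12 weeks of last dose", with a parallel limit on the steroid dose. No event type is excepted.
- **Myocarditis row:** "Myocarditis Grade 1 or 2 Withhold". Grade 3 or 4 means permanent discontinuation. The row has no resumption condition of its own.
- **Hypophysitis row:** "Hypophysitis Grade 2 Withhold". For Grade 3 or 4 the action is "Withhold or permanently discontinue", which footnote 1 leaves to the investigator or treating physician.
- **NOTE under the table:** it opens "For subjects with Grade 3 or 4 immune-related endocrinopathy where withhold of pembrolizumab is required" and allows resumption at Grade 2 or below when the event is under control on hormone replacement, or metabolically controlled in the case of type 1 diabetes (T1DM).

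**The concern.** A withholding table has to map each clinical state to one action. In two places this one does not.

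For myocarditis, the grades at which dosing stops and the grades at which it may restart share Grade 1. One site could read the row and keep withholding while another reads instruction 2 and restarts, and both could cite the table.

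For hypophysitis, two subjects in the same present condition are treated differently because of how severe the event was at onset, and the one with the milder history faces the lower grade threshold. The table gives no reason, and it looks like an omission from the scope of the NOTE.

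What is at stake is subject safety and uniform application of a binding rule. Section 5.8 sends mandatory discontinuation for unacceptable adverse experiences back to Section 5.2.1.2, and safety and tolerability is a primary objective (Section 3.1).

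**Working it through.** The plan states no figure on this point and no arithmetic applies. The check compares the grades that trigger withholding in each Table 4 row with the grades at which a resumption rule releases the subject. The inputs are the Table 4 rows, General instruction 2 (release at Grade 0 or 1, steroid tapered) and the NOTE (release at Grade 2 or below with control, for Grade 3 or 4 endocrinopathy).

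| Row | Withheld at | Released at | Result |
|---|---|---|---|
| Pneumonitis | 2 | 0–1 | No overlap |
| Diarrhea/colitis | 2–3 | 0–1 | No overlap |
| AST/ALT/bilirubin | 2 | 0–1 | No overlap |
| Nephritis | 2 | 0–1 | No overlap |
| **Myocarditis** | **1–2** | **0–1** | **Overlap at Grade 1** |
| **Hypophysitis, began at 2** | **2** | **0–1** | **Not released at Grade 2** |
| **Hypophysitis, began at 3–4, withheld** | **3–4** | **≤2 if controlled** | **Released at Grade 2** |
| Hyperthyroidism | 3–4 (Grade 2 continues) | ≤2 if controlled | Consistent |
| Hypothyroidism | Never (Grades 2–4 continue) | Not needed | Consistent |

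**Myocarditis.** The common element of {1, 2} and {0, 1} is Grade 1, and it arises in two ways.

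1. *Onset at Grade 1.* The row withholds, yet the subject is already at a grade that instruction 2 accepts for resumption. The row ties steroid use to severity, so there may be no taper to wait for.
2. *Onset at Grade 2, settling at a persistent Grade 1.* Once any taper is complete, instruction 2 permits dosing, while the subject's current grade is still one the row lists for withholding.

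**Hypophysitis.** Take two subjects, both now at Grade 2 and controlled on hormone replacement.

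- Subject X began at Grade 3 and was withheld, not discontinued. The NOTE applies and X may resume.
- Subject Y began at Grade 2 and was never worse. The NOTE does not apply. Instruction 2 does, and Y must reach Grade 1 or 0 with steroid tapered.

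The highest grade allowed at resumption is 2 for X and 1 for Y, a difference of one grade against the milder course.

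**Other sections.** Section 5.6 (supportive care), Section 5.8 (discontinuation) and Section 7.1.1.8 (interruptions) give no resumption grade that would settle either case.

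**The case against.** The best defence on myocarditis is that the rules are sequential: the row says when to stop, and instruction 2 says when a stopped subject may restart. Its wording about the event being reduced suggests improvement, it is permissive, and it also requires the taper. That is a reasonable reading of a Grade 2 event that improves. It does not settle a Grade 1 onset: if improvement is required, such a subject would have to reach Grade 0, which the table does not say. Nor does anything limit the row to new events, so a subject restarted at a persistent Grade 1 is still in a listed withholding grade.

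On hypophysitis, the NOTE is a specific exception, and an exception may override a row. That stands: resumption at Grade 2 after a Grade 3 or 4 event does not contradict the Grade 2 row. It is also fair that Grade 3 or 4 hypophysitis carries a discretionary discontinuation option that Grade 2 lacks, and that the NOTE adds a control requirement absent from instruction 2. So the milder event is not treated more harshly in every respect. What remains is the unexplained difference in resumption grade between subjects in the same current state.

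A reader might infer more than the text supports:

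- *That T1DM below Grade 3 is shut out of the NOTE.* The row's trigger is "Newly onset T1DM or Grade 3 or 4 hyperglycemia associated with evidence of" β-cell failure. The documents assign no grade to T1DM, and the NOTE names it.
- *That Grade 2 endocrinopathy in general is affected.* Grade 2 hyperthyroidism and hypothyroidism continue treatment. Among the named rows only hypophysitis is caught.
- *That at 12 weeks Subject Y is stopped for good while X carries on.* The NOTE does not say that it lifts the 12-week limit, and Section 7.1.1.8 provides for interruptions beyond 12 weeks by documented agreement between investigator and sponsor.
- *That duration of response or progression-free survival would shift.* No event rates are given, so no effect can be shown.

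Section 5.6 refers to a separate guidance document on events of clinical interest for more detail. It is not among the documents, and it may or may not address these cases. Either way, the protocol table should not need it to be consistent.

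**Conclusion.** The point holds in two specific places. In the myocarditis row, Grade 1 is both a withholding and a resumption grade. This is clearest at Grade 1 onset and also present when a Grade 2 event settles at Grade 1. In the hypophysitis row, a subject at controlled Grade 2 may or may not resume depending only on whether the event began at Grade 3–4 (and was withheld) or at Grade 2.

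The size is one shared grade in one row and a one-grade gap in one other. The number of subjects cannot be estimated from the documents and may be small. Sample size, confidence intervals and interim decision rules are unaffected. The matter deserves correction because it bears on subject safety and the table is binding on sites.

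The conclusion assumes that the row grades are read as current grades unless the table says otherwise, that instruction 2 covers every withheld event because it excepts none, and that no site-facing document already resolves the two cases.

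**What to change.** Reconcile General instruction 2, the NOTE, and the myocarditis and hypophysitis rows of Table 4, so that each state a subject can be in leads to one action. The revised text should make clear whether each rule is read on the grade at onset or the current grade, and the guidance document on events of clinical interest should be checked for agreement with it. The clinical team decides the content; no grade or rule is proposed here.

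The cost is table wording in an amendment or a clarification letter to sites. No visit, procedure or analysis changes.

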5.2.2 Timing of Dose Administration

Pembrolizumab should be administered on Day 1 of each three week cycle after all procedures/assessments have been completed as detailed on the Trial Flow Chart (Section 6.0). On Cycle 1 Day 1 trial treatment should begin on the day of allocation or as close as possible to the date on which the subject is allocated/assigned. After Cycle 1 Day 1, trial treatment may be administered up to 3 days before or 3 days after the scheduled Day 1 of each cycle due to administrative reasons.

Pembrolizumab 200 mg will be administered as a 30 minute IV infusion every 3 weeks. Sites should make every effort to target infusion timing to be as close to 30 minutes as possible. However, given the variability of infusion pumps from site to site, a window of -5 minutes and +10 minutes is permitted (i.e., infusion time is 30 minutes: -5 min/+10 min).

The Pharmacy Manual contains specific instructions for pembrolizumab dose calculation, reconstitution, preparation of the infusion fluid, and administration.

5.2.3 Trial Blinding/Masking

This is an open-label trial; therefore, the Sponsor, investigator, site personnel, and subject will know the treatment administered.

The subject-level PD-L1 biomarker results in Cohort A will be masked in the database to the investigator and the study team at the Sponsor including clinical, statistical, statistical programming, and data management personnel. Access to the PD-L1 subject-level biomarker results will be limited to designated team at the Sponsor (see Section 8.2.1) who will be responsible for data review to ensure validity of results but who will have no other responsibilities associated with the study.

5.3 Randomization or Treatment Allocation

Centralized interactive voice response system / integrated web response system (IVRS/IWRS) will be utilized. Subjects will be assigned to all study therapies in an unblinded fashion. Subjects participating in this trial will be allocated by non-random assignment.

5.4 Stratification

No stratification based on age or other characteristics will be used in this trial.

5.5 Concomitant Medications/Vaccinations (Allowed & Prohibited)

Medications or vaccinations specifically prohibited in the exclusion criteria are not allowed during the ongoing trial. If there is a clinical indication for any medication or vaccination specifically prohibited during the trial, discontinuation from trial therapy or vaccination may be required. The investigator should discuss any questions regarding this with the Sponsor Clinical Director. The final decision on any supportive therapy or vaccination rests with the investigator and/or the subject's primary physician. However, the decision to continue the subject on trial therapy or vaccination schedule requires the mutual agreement of the investigator, the Sponsor and the subject.

